2.3. Purpose of the Analysis

The current clinical study has two major objectives. First, to further characterize and better understand whether innate immune responses as measured at early time points following vaccination with ChAd-EBO-Z are associated with late endpoints such as neutralizing antibody titers, T cell responses, and potentially protection from EVD. Second, to evaluate the effect of homologous or heterologous boosting, with a short interval employed between prime and boost vaccination. The advantage of the short interval is that it minimizes the risk of post-immunization anti-vector (ChAd3) antibodies interfering with the boost response and differs from other studies such as 14-day intervals as tested in NCT02451891 in which the adaptive response had already evolved significantly. A short interval also has the potential advantage of accelerating the development of immune responses for those at risk in an outbreak setting or for aid workers deployed to outbreak areas. This trial will employ systems biology tools [28], in addition to immunology and clinical chemistry methods, to explore whether the kinetics, magnitude and profile of host responses following first and second vaccination can provide insights into potential mechanisms of protection and the differences between protective and non-protective states.

3. STUDY OBJECTIVES AND ENDPOINTS

3.1. Study Objectives

3.1.1. Primary

- Assess the safety and reactogenicity of study products by study group when administered IM to healthy adults.

3.1.2. Secondary

- Assess the antibody response to Zaire ebolavirus (EBOV) glycoprotein (GP) by study group.

3.1.3. Exploratory

- Assess the EBOV neutralizing antibody titers by study group.
- Assess antibody functionality by antibody-dependent cell-mediated cytotoxicity (ADCC) responses by study group.
- Assess activation of CD4+ and CD8+ T cells in multiple cell subpopulations by study group.
- Assess inflammation via cytokine secretion and C-reactive protein (CRP) by study group.
- Assess EBOV GP-specific T cell responses by study group.
- Assess ChAd3-specific T cell responses by study group.
- Assess plasmablast frequencies by study group.
- Assess B-cell receptor (BCR) repertoire by study group.
- Assess and characterize change in gene expression in PBMCs by study group.
- Identify gene expression changes associated with adaptive humoral and/or cellular immune responses.

3.2. Study Outcome Measures

3.2.1. Primary

- Frequency and severity of solicited local and systemic reactogenicity from the time of study vaccine administration through 7 days post-vaccination.
- Frequency and severity of vaccine-related unsolicited adverse events (AEs) from the first study vaccination through 28 days post second vaccination.
- Frequency and severity of clinical safety laboratory AEs from the time of first study vaccination through approximately 28 days after the second vaccination.
- Frequency of Serious Adverse Events (SAEs) and vaccine-related Medically Attended Adverse Events (MAAEs) through 6 months post first vaccination.

3.2.2. Secondary

- Seroconversion defined as anti-EBOV GP ELISA titer > 50 if baseline (Day 1) titer ≤ 50 or fold rise ≥ 4 as compared to baseline if baseline titer > 50 on Day 8, 15, 22, 29 and 36.
- Geometric mean titer (GMT) on Day 1, 8, 15, 22, 29 and 36 as measured by anti-EBOV GP ELISA.
- Geometric mean fold rise (GMFR) in titer on Day 8, 15, 22, 29 and 36 compared to baseline (Day 1) as measured by anti-EBOV GP ELISA.

3.2.3. Exploratory

- GMT of neutralizing antibodies to EBOV GP at Day 1, 8 and 15 as measured by EBOV GP pseudovirion neutralization assay.
- GMFR in titer on Day 8 and 15 compared to baseline (Day 1) as measured by EBOV GP pseudovirion neutralization assay.
- Change in the percentage of killed cells as measured by ADCC on Day 8, 15, 22, 29, and 36 compared to baseline (Day 1).
- Change in percentage of activated CD4+ and CD8+ T cells for each cell subpopulation on Day 8 and 15 compared to baseline (Day 1) as measured by flow cytometry.
- Change in cytokine concentration and CRP on Day 2, 3, 4, 6, 8, 9 and 15 compared to baseline (Day 1) as measured by Luminex assay and clinical laboratory CRP assay, respectively.
- Change in percentage of EBOV GP-specific cytokine secreting CD4+ and CD8+ T cells on Day 8, 15, 22, and 36 compared to baseline (Day 1) as measured by intracellular cytokine staining (ICS).
- Change in percentage of EBOV GP-specific CD4+ and CD8+ T cells on Day 8 and 15 as compared to baseline (Day 1) measured by tetramer staining for predominant human leukocyte antigen (HLA) types.
- Change in percentage of ChAd3-specific cytokine secreting CD4+ and CD8+ T cells on Day 8, 15, 22 and 36 compared to baseline (Day 1) as measured by ICS.
- Change in percentage of CD19+CD27+CD38+ plasmablasts on Day 8 and 15 compared to baseline (Day 1) as measured by flow cytometry.
- Change in B-cell repertoire (BCR) on Day 8 and 15 as compared to baseline (Day 1) from sorted CD19+ CD27+ CD38+ plasmablasts as measured by immunoglobulin heavy chain sequencing.
- Characterization of antigen-specific BCR as measured by yeast display on day 36.
- Change in gene expression in PBMCs on Day 2, 3, 4, 6, 8, 9, and 15 compared to baseline (Day 1) as measured by RNA-Seq.
- Identification of gene expression changes on Day 2, 3, 4, 6, 8, 9, and 15 associated with each subject's peak change in percentage of EBOV GP-specific cytokine secreting CD4+ and CD8+ T cells across Day 15, 22, and 36.
- Identification of gene expression changes on Day 2, 3, 4, 6, 8, 9, and 15 associated with each subject's peak anti-EBOV GP ELISA titer across Day 15, 22, 29, and 36.

- Identification of gene expression changes on Day 2, 3, 4, 6, 8, 9, and 15 associated with each subject's EBOV neutralizing antibody titer at Day 15.
- Identification of gene expression changes on Day 2, 3, 4, 6, 8, 9, and 15 associated with each subject's peak percentage of killed cells as measured by ADCC across Day 15, 22, 29, and 36.

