8.2.2. Special Assays or Procedures

Immunogenicity testing will include the following (post first vaccination):

- Humoral responses by ELISA and ADCC at Day 1, 8, 15, 22, 29 and 36.
- Humoral response by EBOV GP Neut at Day 1, 8 and 15.
- Cell-mediated immunity assays (EBOV GP T cell response) at Day 1, 8, 15, 22, and 36.
- Cell-mediated immunity assays (ChAd3 vector T cell response) at Day 1, 8, 15, 22 and 36.
- Plasmablasts (5), BCR repertoire analysis (11), CD8 tetramer staining and activation marker analysis at Day 1, 8 and 15.
- Cytokine/chemokine measurement at Day 1, 2, 3, 4, 6, 8, 9, and 15.
- Transcriptomics/Gene expression PBMCs at Day 1, 2, 3, 4, 6, 8, 9 and 15.

- Characterization of antigen-specific BCR as measured by yeast display on day 36.

Venous blood samples will also be collected for future use. 8 mL will be collected on Day 1, 8, 15, 22 and 36 post first vaccination. 42 ml will be collected on Day 182 post first vaccination. Collection of future use samples is a condition of participation in this study.

The volume (ml) of venous blood to be collected for immunogenicity assays and future research is presented in [Table 2](#).

Table 2: Blood Volumes (ml)

Study Visit (V)	0	1	2	3	4	5	6	7	8	9	10	11	12	13	14	US	ED
Study Day (from Vaccine 1)	<-29	1	2	3	4	6	8	9	15	22	29	36	76	106	182		
Screening Lab	14.2																
Clinical Safety Evaluations		6.5					6.5		6.5		6.5	6.5				6.5^	6.5^
High Resolution HLA typing for Class 1 (A, B, C locus)		6.0															
Humoral response – ELISA (Op 2)																	
Humoral response – ADCC (Op 7)		10.0						10.0		10.0	10.0						10.0^
Humoral Response, EBOV GP Neut Antibody (Op7a)																	
EBOV GP T cell responses (Op 3)		24.0						24.0		24.0	24.0		24.0				
ChAd3 vector T cell responses (Op 4)																	
Plasmablasts (Op 5, 11)		32.0					32.0		32.0								
Cd8 Tetramer Staining (Op 9)			8.0														8.0*
Activation Marker Analysis (Op 10)								8.0		8.0							
Exploratory cytokine/chemokine (Op 6)		5.0	5.0	5.0	5.0	5.0	5.0	5.0	5.0								
Transcriptomics PMBCs (Op 8)		16.0	16.0	16.0	16.0	16.0	16.0	16.0	16.0								
Yeast Display													16.0				
Future Use		8.0					8.0		8.0	8.0		8.0		42.0			
Total per visit	14.2	115.5	21.0	21.0	21.0	21.0	109.5	21.0	109.5	42.0	16.5	64.5	0.0	0.0	42.0	6.5	14.5-24.5
Running Total	14.2	129.7	150.7	171.7	192.7	213.7	323.2	344.2	453.7	495.7	512.2	576.7	576.7	576.7	618.7	N/A	N/A

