11.4.4. Exploratory Data Analyses

Pre-second vaccination, Study Groups 1, 2, 3 will be analyzed jointly as one study group as all three study groups received the same vaccine at Day 1.

GMT of neutralizing antibodies to EBOV GP at Day 8 and 15 and GMFR in titer on Day 8 and 15 compared to baseline (Day 1) and associated 95% CIs will be calculated and summarized as described in [Section 11.4.3](#). Significant differences in neutralizing antibodies to EBOV GP or Anti-EBOV GP ELISA titer between study groups for each post-second vaccination time points will be evaluated using a two-sided Welch's T-test using an individual alpha of 0.05. Differences in Anti-EBOV GP ELISA-based seroconversion at post-second vaccination time points will be assessed using a two-sided Fishers' exact test using an individual alpha of 0.05.

Baseline fold changes for³⁵ percentage of killed cells³⁶ percentage of activated CD4+ and CD8+ T cells³⁷, cytokine concentrations³⁸, percentage of EBOV GP-specific cytokine secreting CD4+ and CD8+ T cells expression one, two, or multiple makers³⁹, percentage of EBOV GP-specific CD4+ and CD8+ T cells⁴⁰, percentage of ChAd3-specific cytokine secreting CD4+ and CD8+ T cells⁴¹, percentage of CD19+CD27+CD38+ plasmablasts will be summarized using minimum, Q1, median, Q3, maximum, and 95% CI of the median. The 95% CI of the median fold change from baseline will be determined by using the bootstrap method and visualized using time trend plots. To identify features that show a differential response from baseline, a two-sided Wilcoxon signed-rank test will be carried out for each study group using an individual alpha of 0.05. Significant differences in fold changes between study groups for post-second vaccination time

points will be evaluated using a two-sided Wilcoxon rank-sum test using an individual alpha of 0.05.

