For the transcriptomics exploratory analysis, RNA-Seq data will be pre-processed by removing adapters and low-quality reads and mapping sequences to the latest human reference genome using splice-aware alignment software such as *HISAT2*³⁵. Gene expression quantification will be carried out by using the *Subread* software³⁶ using the latest Ensembl³⁷ gene model annotations as a reference. Systematic differences in sequence coverage between samples will be accounted for using the TMM method³⁸ as implemented in the *edgeR*³⁹ R package. Principal component analysis, non-metric multidimensional scaling, and hierarchical clustering analysis will be used to identify potential global outliers and systematic batch effect. Negative binomial models as implemented in *edgeR*³⁹ will be used to identify genes for each study group and post-vaccination day that were differentially expressed (DE) compared to pre-vaccination as well as genes that were DE between study groups. If the analysis reveals a systematic batch effect that is not associated with study group, it will be accounted for by adding a batch blocking factor as part of the negative binomial models. To control for testing multiple genes, the false-discovery rate (FDR) based on the Benjamini-Hochberg procedure⁴⁰ as implemented in the *p.adjust* R function will be applied. Genes with a FDR-value < 0.05 and a fold change of greater or equal to 1.5-fold (up or down regulation) will be deemed to be significantly DE. Depending on observed treatment effects, this fold change cut off may be revised. The *pvclust*⁴¹ R package will be applied to identify co-expressed DE gene clusters and cluster time trends will be visualized. Pathway enrichment analysis based on the latest MSigDB⁴² and KEGG⁴³ databases as well as Blood Transcription Modules⁴⁴ accounting for gene length bias will be carried out using the implementation provided by the *goseq*⁴⁵ R package. Pathway maps color-coded by treatment effect will be provided for significantly enriched KEGG pathways. Regularized canonical correlation analysis and regularized linear regression analysis as implemented in the mixOmics⁴⁶ and *glmnet*⁴⁷ R packages, respectively will be utilized to identify gene expression changes that are associated with adaptive humoral and/or cellular immune response endpoints. In both cases, cross-validation will be used to select optimal models.

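### The ADCC gene-association outcome leaves the scheduled Day 1 killing value unused; entering it as a covariate would be a near-free improvement to an exploratory analysis

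*SAP*

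**What the plan says.** SAP 3.2.3 and Protocol 3.2.3 list four outcomes to which gene expression changes will be related:

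- ADCC: "peak percentage of killed cells as measured by ADCC across Day 15, 22, 29, and 36"
- T cells: "peak change in percentage of EBOV GP-specific cytokine secreting CD4+ and CD8+ T cells across Day 15, 22, and 36"
- ELISA: "peak anti-EBOV GP ELISA titer across Day 15, 22, 29, and 36"
- Neutralization: "EBOV neutralizing antibody titer at Day 15"

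Only the T-cell outcome is a change. The stand-alone ADCC endpoint in the same list is also a change from Day 1. Protocol 11.4.4 puts percentage of killed cells first among the measures to be summarised as "Baseline fold changes for" the listed assays.

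Day 1 ADCC is scheduled: Protocol 8.2.2 has "Humoral responses by ELISA and ADCC at Day 1, 8, 15, 22, 29 and 36". Protocol 11.4.4 says that regularized canonical correlation and regularized linear regression (mixOmics and glmnet) will be used to find "gene expression changes that are associated with adaptive humoral and/or cellular immune response endpoints", and it names no Day 1 response term. SAP 6.4 plans no covariate adjustment of the immunogenicity analyses. SAP 1 (Preface) sends the systems biology analyses to a SAP addendum, which is not among the documents.

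**The concern.** The Day 1 sample is taken before the first vaccination, and the eligibility criteria exclude Ebola vaccination, disease and known exposure. Killing measured on Day 1 therefore cannot be a response to the study vaccines. If part of it is stable within a subject, that part is carried into every later value and so into the peak. A non-responder with high background can then rank above a responder with low background.

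For a model meant to explain response, that spread is noise in the outcome. It weakens true gene associations in an analysis of at most 60 subjects and very many genes. The Day 1 value could remove part of the noise, and the outcome as worded does not use it.

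**Working it through.** **Plan's own figure.** There is none. The trial has no power calculation and the documents report no Day 1 ADCC values, so the size can only be shown over assumed inputs.

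**Inputs.** From the documents: n = 60. Assumed:

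- ρ, the correlation of one gene with the true ADCC response: 0.45 unless noted.
- b, the SD of background killing divided by the SD of response: 0.25 to 1.5.
- s, the correlation between a subject's background on Day 1 and at the peak (stability): 0.3 to 0.8.

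The gene change is taken as unrelated to background. The response SD is set to 1.

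**Formulas.** The correlation that the analysis sees is

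- raw peak: ρ / √(1 + b²)
- peak with Day 1 as covariate: ρ / √(1 + b²(1 − s²))
- peak minus Day 1: ρ / √(1 + 2b²(1 − s))

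Approximate power for one gene is Φ(atanh(r)·√(n − 3 − k) − z), with k = 1 when Day 1 is a covariate and k = 0 otherwise. z is 1.96 for two-sided 0.05 and 3.29 for two-sided 0.001.

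**One case worked through (b = 1, s = 0.8).**

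- Raw: r = 0.45/√2 = 0.318. Power = Φ(0.330 × √57 − 1.96) = 70%.
- Covariate: r = 0.45/√1.36 = 0.386. Power = Φ(0.407 × √56 − 1.96) = 86%.

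**Range.**

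| ρ, alpha | b | s | Raw peak | Day 1 covariate | Peak minus Day 1 |
|---|---|---|---|---|---|
| 0.45, 0.05 | 0.25 | 0.8 | 94% | 95% | 95% |
| 0.45, 0.05 | 0.5 | 0.8 | 90% | 93% | 93% |
| 0.45, 0.05 | 1.0 | 0.8 | 70% | 86% | 86% |
| 0.45, 0.05 | 1.5 | 0.8 | 49% | 74% | 73% |
| 0.45, 0.05 | 1.0 | 0.5 | 70% | 76% | 70% |
| 0.45, 0.05 | 1.0 | 0.3 | 70% | 72% | 62% |
| 0.45, 0.05 | 1.5 | 0.3 | 49% | 51% | 40% |
| 0.55, 0.001 | 1.0 | 0.8 | 42% | 71% | 70% |

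Simulation of the same model (3,000 runs per cell) agrees to within about 3 points wherever it was run. For example, it gives 71% against 87% at b = 1.0, s = 0.8, and 49% against 75% at b = 1.5, s = 0.8.

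**Peak as a maximum.** The table treats the peak as a single value. With the peak simulated as the largest of four visits, the pattern holds. At b = 1.0, s = 0.8, power is 74% raw and 90% with the covariate. At b = 1.0, s = 0.3, the change score gives 71% against 80% raw.

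**Reading.** The covariate matches or beats the raw peak in every row, because 1 − s² never exceeds 1 and the single degree of freedom costs almost nothing. The change score beats the raw peak only when 2(1 − s) < 1, that is, when s > 0.5.

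**The case against.** **The governing document is missing.** The lines in 3.2.3 are outcome labels, and the model specification sits in the addendum, which may already adjust for Day 1. The assay may also subtract background. This stands: a reader might infer that no Day 1 correction is planned at all, and the documents do not show that. They show only that the stated outcome omits one and that no available text adds it.

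**ADCC is not the odd one out.** All three humoral association outcomes are levels, and the T-cell outcome is the exception. Attained activity is also a legitimate target. This stands against reading the ADCC wording as a unique slip. What remains is that the ADCC endpoint itself is referenced to Day 1, and no reason is given for the different scale here.

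**The size is assumed.** Nothing in the documents favours a ratio of 1.0 to 1.5 over 0.25 to 0.5. Planning a fold change presupposes usable, non-zero Day 1 values but says nothing about their spread. The calculation also tests one gene with arms pooled, whereas the plan is cross-validated glmnet and canonical correlation. All of this stands, so the figures illustrate direction and range and do not predict the trial's loss.

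**False genes.** A reader might infer that genes tracking background killing will enter the signature. No scenario tested links background to gene changes, and the predictors are changes from Day 1, which remove stable baseline expression. The supported harm is weakened true associations.

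**Importance.** The trial's first stated objective names neutralizing titers and T-cell responses as late endpoints, not ADCC, and the systems biology results are meant to generate hypotheses. This stands and keeps the severity low.

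**Conclusion.** The point holds as a low-severity, near-free improvement to one exploratory analysis. Both documents define the ADCC association outcome as a raw peak and leave unused a Day 1 value scheduled for every subject. If stable background killing varies between subjects, this weakens true gene associations. With background SD from 0.25 to 1.5 times the response SD, the power gain from a Day 1 covariate runs from essentially none to about 25–30 points. The top of that range needs stable background (s = 0.8) at a ratio of 1.0 to 1.5. With a small or unstable background the gain is a few points at most. The actual position in that range is unknown, and no primary or secondary conclusion is affected.

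Two stronger readings should be resisted. Redefining the outcome as peak change, to match the T-cell outcome, looks natural but loses power when Day 1 killing is unstable (62% against 70% raw at b = 1.0, s = 0.3). The mismatch is also not evidence of an error confined to ADCC.

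**What to change.** Keep peak percentage of killed cells as the outcome. In the glmnet regression, enter Day 1 killing as an unpenalised covariate. In the canonical correlation analysis, use the residual of peak killing regressed on Day 1 killing. State this in the outcome definition (Protocol 3.2.3 and SAP 3.2.3) and in the SAP addendum. If the addendum already handles Day 1, align the outcome wording with it. The addendum should also say whether the ELISA and neutralization association outcomes are deliberately left as levels.

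The cost is one line of text and one degree of freedom. No new samples or assays are needed.

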3.3. Study Definitions and Derived Variables

Safety variables are described in Section 4.5.1 of this document. For endpoints to assess antibody responses against Ebola virus glycoproteins using an ELISA (anti-EBOV GP ELISA), the following seroconversion definition will be applied:

- Anti-EBOV GP ELISA titer > 50 if baseline (Day 1) titer ≤ 50 or fold rise ≥ 4 as compared to baseline if baseline titer > 50 on Day 8, 15, 22, 29 and 36.

4. INVESTIGATIONAL PLAN

4.1. Overall Study Design and Plan

This is a Phase 1, randomized, double-blind trial of 60 males and non-pregnant females, 18-45 years old, inclusive, who are in good health and meet all eligibility criteria. This trial was designed to assess the safety, reactogenicity and immunogenicity of a *Zaire ebolavirus* vaccine (ChAd3-EBO-Z) for the prevention of EVD. Vaccine will be administered intramuscularly in a single dose regimen on Day 1 followed by a booster dose at Day 8 for all groups (group 1: placebo boost, group 2: ChAd3-EBO-Z boost, group 3: MVA-BN®-Filo boost). Potential subjects were screened by history, physical exam, vital signs, height and weight, and clinical laboratory tests prior to enrollment. Subjects were randomized in double-blind fashion to one of three vaccine schedules: 1 dose of ChAd3-EBO-Z vaccine at Day 1 followed by a booster dose at Day 8 ([Table 1](#)).

4.2. Discussion of Study Design, Including the Choice of Control Groups

This was a double-blind clinical trial. Subjects, investigators, study personnel performing any study-related assessments were blinded to treatment arm assignment (i.e., type of booster). The inclusion of the Placebo boost allows for the assessment of the boosting effect for Study Arms 2 and 3 relative to a single dose (Study Arm 1) accounting for any Dose 1-related effects that extended beyond Day 8.

4.3. Selection of Study Population

Sixty males and non-pregnant females, 18-45 years old, inclusive, who are in good health and meet all eligibility criteria, were enrolled from a single Vaccine and Treatment Evaluation Unit (VTEU) site. The target population was to reflect the community at large at the participating VTEU site. Estimated time to complete enrollment in this trial was approximately 5 months. Information regarding this trial was provided to potential subjects who have previously participated in vaccine trials conducted at the participating VTEU site. Other forms and/or mechanisms of recruitment might also have been used.

4.3.1. Subject Inclusion Criteria

Subjects eligible to participate in this study must meet all of the following inclusion criteria:

1. Provide written informed consent before initiation of any study procedures.
2. Are able to understand and comply with planned study procedures and be available for all study visits/phone calls.
3. Males or non-pregnant females ages 18-45, inclusive.
4. Subject must have a body mass index (BMI) ≥ 18.5 and $< 35 \text{ kg/m}^2$.
5. Are in good health*

* As determined by medical history and physical examination to evaluate acute or currently ongoing chronic medical diagnoses or conditions, defined as those that have been present for at least 90 days which would affect the assessment of the safety of subjects or the immunogenicity of study vaccinations. Chronic medical diagnoses or conditions should be stable for the last 60 days (no hospitalizations, ER or urgent care for condition and no adverse symptoms that need medical intervention such as medication change/supplemental oxygen). This includes no change in chronic prescription medication, dose, or frequency as a result of deterioration of the chronic medical diagnosis or condition in the 60 days prior to enrollment. Any prescription change that is due to change of health care provider, insurance company, etc., or that is done for financial reasons, as long as in the same class of medication, will not be considered a deviation of this inclusion criterion. Any change in prescription medication due to improvement of a disease outcome, as determined by the site

principal investigator or appropriate sub-investigator, will not be considered a deviation of this inclusion criterion. Subjects may be on chronic or as needed (prn) medications if, in the opinion of the site principal investigator or appropriate sub-investigator, they pose no additional risk to subject safety or assessment of reactogenicity and immunogenicity and do not indicate a worsening of medical diagnosis or condition. Similarly, medication changes subsequent to enrollment and study vaccination are acceptable provided there was no deterioration in the subject's chronic medical condition that necessitated a medication change, and there is no additional risk to the subject or interference with the evaluation of responses to study vaccination. Note: Topical, nasal, and inhaled medications (apart from steroids as outlined in the Subject Exclusion Criteria), herbals, vitamins, and supplements are permitted.

6. Oral temperature is less than 100.0 °F (37.8°C).
7. Pulse is 47 to 105 beats per minute (bpm), inclusive.
8. Systolic blood pressure (BP) is 85 to 150 mm Hg, inclusive.
9. Diastolic blood pressure (BP) is 55 to 95 mm Hg, inclusive.
10. Have acceptable screening laboratories^{#&} within 28 days prior to enrollment (Refer to Appendix C in the protocol for acceptable screening values.)

#Screening labs include white blood cell (WBC), Hgb, platelet count, ANC, sodium, potassium, creatinine, albumin, total protein, PT, PTT, alanine aminotransferase (ALT). Blood Urea Nitrogen (BUN) will be obtained only if creatinine is above normal range.

&Screening laboratory values that are outside the range of eligibility but are thought to be due to an acute condition or due to laboratory error may be repeated once. [see Manual of Procedures (MOP)]

11. Have normal screening laboratories for urine protein. Trace protein is acceptable.
12. Drug screen for opiates is negative.
13. Hemoglobin A1C (HgbA1C) <6.3% at screening.
14. HIV 1/2 antibody negative.
15. HCV antibody negative.
16. HBsAg negative.
17. Women of childbearing potential[‡], must be using an effective method of contraception[§] from 30 days prior to the first study vaccination until 90 days after the second study vaccination.

‡ Not sterilized via tubal ligation, bilateral oophorectomy, hysterectomy, successful Essure® placement (permanent, non-surgical, non-hormonal sterilization) with history of documented radiological confirmation test at least 90 days after the procedure (or with use of another birth control method if history of confirmation test not confirmed), still menstruating, or < 1 year of the last menses if menopausal.

§ Includes, but is not limited to, non-male sexual relationships, abstinence from sexual intercourse with a male partner, monogamous relationship with a vasectomized partner, male condoms with the use of applied spermicide, intrauterine devices, NuvaRing®, and licensed hormonal methods such as implants, injectables or oral contraceptives ("the pill").

18. Women of childbearing potential must have a negative serum pregnancy test at screening and a negative urine pregnancy test within 24 hours prior to each study vaccination.
19. Women agree to not donate eggs (ova, oocytes) from the start of screening onwards until at least 90 days after the second vaccination.
20. Agrees not to participate in another clinical trial during the study period.
21. Agrees not to donate blood to a blood bank for 3 months after receiving the second study vaccine.

